## 10.4 POOLING OF SITES

Not applicable.

## 10.5 MULTIPLE COMPARISONS

Not applicable.

## 10.6 SUBGROUP ANALYSES

Not applicable.

## 10.7 STATISTICAL ISSUES

None.

# 11 STATISTICAL OUTPUT

General principles for layout of the statistical output are described in Section 10.1. Layout and specifications are illustrated for each unique table and listing within the shells presented in Section 14.

## 11.1 SUBJECT DISPOSITION

The subject disposition table will summarise the following data for all randomised subjects:

- The number (%) of subjects within each analysis set;
- The number (%) of subjects receiving each treatment;
- The number (%) of subjects within each treatment schedule (sequence);
- The number (%) of subjects who completed each study period, where completion is defined as having the 48 h sample collections on Day 3 (Period 1) or Day 5 (Period 2).
- The number (%) of subjects who completed the study/withdrew from the study and the associated reasons for early study termination. A subject is deemed to have completed the study if they complete the Post-Study follow-up telephone contact.

Screening and study completion/termination data will also be listed. A listing of all subjects with protocol deviations will be presented including major/minor classification. A data listing presenting subject eligibility for each analysis set and the reason for exclusion from an analysis set will also be presented.

## 11.2 SUBJECT CHARACTERISTICS AT BASELINE

### 11.2.1 Demographic and Baseline Characteristics

Demographic data will be listed (including informed consent information) and descriptive statistics for the continuous variables age, height, weight and BMI and frequencies for the categorical variable race will be tabulated by gender and overall.

Demographic and baseline data will be listed and summarised using the Safety Set. Demographic data may also be summarised using the PK Set/Urine Excretion Set, if appropriate.

## 11.3 EFFICACY ANALYSES

Not applicable.

## 11.4 PK ANALYSES

The primary analysis sets for summaries of plasma and urine PK data will be the PK Set and Urine Excretion Set respectively. If the PK Set/Urine Excretion Set and the Safety Set are not equivalent, then all PK summaries described below will also be produced for the Safety Set.

### 11.4.1 Plasma Concentration Data

Plasma PK samples will be collected for measurement of cytosine at the following time points during each period: Pre-dose, 15 min, 20 min, 30 min, 45 min, 1h, 1.5h, 2h, 2.5h, 3h, 4h, 6h, 8h, 12h, 14h, 16h, 24h and 48h post-dose.

Cytosine concentrations in plasma will be listed and summarised for each treatment using the descriptive statistics N, n, arithmetic mean, arithmetic standard deviation (SD), coefficient of variation (CV%), minimum, median and maximum.

The individual subject plasma cytosine concentration profiles over time will be presented graphically using actual blood sampling times on a linear and semi-logarithmic scale for each subject with both treatments

presented on the same plot. Arithmetic mean plasma cytosine concentration profiles over time will be presented on linear and semi-logarithmic scales.

For inclusion within the summary tables and linear scale plots, concentrations below the limit of quantification (BLQ) will be assigned a value of zero. Concentrations above the upper limit of quantification (ULOQ) will be obtained via dilution into the calibration range and are valid results. For inclusion within the semi-logarithmic scale plots, concentrations below the limit of quantification will be set to missing.

Plasma concentration data listings and individual plots will be presented using the Safety Set. Plasma concentration data summaries and mean plots will be presented using the PK Set and also the Safety Set if it differs from the PK Set. All plasma concentration data included in listings and summaries will be presented to three significant figures.

#### 11.4.2 Derived Plasma PK Parameters

The following derived pharmacokinetic parameters of cytosine in plasma will be determined using WinNonlin Phoenix 6.4 from the individual concentration versus time profiles using standard non-compartmental methods:

Pharmacokinetic Parameter	Definition	WinNonlin computation	WinNonlin Parameter Name
$C_{max}$ (ng/mL)	Maximum observed plasma concentration post dose	Maximum observed concentration, occurring at $T_{max}$ . If not unique, then the first maximum is used.	Cmax
$T_{max}$ (h)	Time of occurrence of maximum observed plasma concentration	Time of maximum observed concentration. If the maximum observed concentration is not unique, then the first maximum is used.	Tmax
$AUC_{0-t}$ (h*ng/mL)	The area under the plasma concentration-time curve (AUC) from 0 h to the last sampling time at which concentrations were at or above the LLOQ	AUC measured from the concentration at time of dosing to the last measurable positive concentration. The AUC is computed using the linear-up/log-down trapezoidal method.	AUClast
$AUC_{(0-inf)}$ (h*ng/mL)	The AUC from 0 h extrapolated to infinity	AUC measured from the concentration at time of dosing extrapolated to infinity based on the last observed concentration. $= AUC_{0-t} + \frac{C_{lastobs}}{\lambda_z}$	AUCINF_obs
$AUC_{\% \text{ extrapolated}}$ (%)	Residual area.	Percentage of $AUC_{0-inf}$ due to extrapolation from time of last measurable positive concentration to infinity. $= \frac{AUC_{0-inf} - AUC_{0-t}}{AUC_{0-inf}} \cdot 100$	AUC_%Extrap_obs
$\lambda_z$ (1/h)	Apparent terminal elimination rate constant.	First order rate constant associated with the terminal (log-linear)	Lambda_z

		portion of the curve. Estimated by linear regression of time vs. log concentration; the regression analysis should contain data from at least 3 different time points in the terminal phase.	
$t_{1/2}$ (h)	Apparent terminal elimination half-life.	$= \ln(2) / \lambda_z$	HL_Lambda_z
CL/F	Apparent total body clearance.	$= Dose / AUC_{0-inf}$	Cl_F_obs
Vd/F	Apparent volume of distribution based on the terminal phase.	$= \frac{Dose}{K_{el} \cdot AUC_{0-inf}}$	Vz_F_obs

The terminal elimination rate constant ( $\lambda_z$ ) will be determined by plotting the concentration data versus time on a semi-logarithmic scale. The parameter will be estimated by linear least square regression analysis, using the last three (or more) non-zero concentrations. The upper and the lower time points, as well as the number of time points, used for  $\lambda_z$  estimation will be reported. Values of  $\lambda_z$ ,  $AUC_{0-\infty}$ , %AUC and  $t_{1/2}$  will not be reported for cases where  $\lambda_z$  cannot be reliably determined.

$AUC_{0-t}$  will be calculated using the linear-up/log-down trapezoidal method.

For the calculation of derived pharmacokinetic parameters, concentrations below the limit of quantification (BLQ) will be assigned a value of zero. In case of a deviation from the theoretical time, the actual time of blood sample will be used in the calculation of the derived pharmacokinetic parameters. Should the actual time be unavailable but a blood sample was taken, the nominal time point will be assigned.

Derived pharmacokinetic parameters will be listed and summarised for each treatment. The descriptive statistics presented will be N, n, arithmetic mean, arithmetic standard deviation (SD), coefficient of variation (CV%), minimum, median, maximum and geometric mean (with the exception of  $T_{max}$ ).

If no reliable PK parameter can be determined for more than a third of the subjects, only n, minimum and maximum values will be presented for that parameter and all other descriptive statistics will be omitted.

Plasma PK parameter data listings will be presented using the Safety Set. Plasma PK data summaries will be presented using the PK Set and also the Safety Set if they differ. All PK parameter data included in listings and summaries will be presented to three significant figures with the exception of the CV% which will be presented to one decimal place.

#### 11.4.2.1 Statistical Analysis of Plasma PK Parameters

Following logarithmic transformation,  $C_{max}$ ,  $AUC_{0-t}$ , and  $AUC_{0-\infty}$  values will be subjected to an analysis of variance (ANOVA) including fixed effects for sequence (treatment schedule), period, treatment and subject nested within sequence. Point estimates and 90% confidence intervals (CI) will be constructed for the contrasts between fed and fasted states using the residual mean square error obtained from the ANOVA. The point and interval estimates will be back-transformed to give estimates of the ratios of the geometric least squares means (LSmean) and corresponding 90% CI. In addition, estimated geometric means will be presented.

A comparison of  $T_{max}$  will be performed using the Wilcoxon Signed-Rank test. In addition, the Hodges-Lehmann estimate of the median difference in  $T_{max}$  and 95% CI will be presented.

The statistical analysis of the plasma PK parameters will be performed using the PK Set and also the Safety Set if they differ. Geometric LSmeans will be presented to three significant figures and the ratios and 90% CIs will be presented to 2 decimal places.

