A third study (ACH-CYT-01) examined the pharmacokinetic profile of cytisine in healthy non-smoking subjects following administration of 3 mg cytisine in the original marketed formulation during the fed and fasted states. The primary PK outcomes are summarized in (Table 3):

Table 3: ACH-CYT-01 PK Results

	Fasted	Fed
C_{\max}	22.9 ng/mL	22.3 ng/mL
AUC_{0-t}	166 ng.h/mL	160 ng.h/mL
$AUC_{0-\infty}$	173 ng.h/mL	168 ng.h/mL
T_{\max}	0.75 h	2.75 h
$T_{1/2}$	4.59 h	4.77 h

Fasted subjects received a single dose of 3 mg cytisine and approximately 82% of the dose was recovered from urine within 24 hours. Final urinary concentrations in the study were measured in the 12-24 hour epoch and were non-zero for all subjects, indicating that renal excretion was still ongoing beyond 24 hours after cytisine administration. However, based on the diminishing urinary concentrations over time, it can be concluded that excretion is likely to be complete within 48 hours.

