5.2. Discussion of Study Design

This study design minimizes the influence of inter-subject variability, which is assumed to be higher than the intra-subject variability, as each subject will be administered cytisine in both the fed and fasted states. As each subject serves as his own control, the precision of the comparison should be improved.

The blood and urine samples for the determination of cytisine plasma and urine concentrations will be collected up to 48 hours after cytisine administration. Taking into account the known terminal elimination half-life of cytisine (about 4 hours), this sampling schedule is expected to provide a reliable estimate of the extent of exposure.

The washout of at least 48 hours between dose administration will allow a complete elimination of cytisine between doses and is deemed sufficiently long to avoid any relevant carry-over effect.

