8.8. Selection and Timing of Dose for Each Subject

Doses will be administered at approximately 9:00 a.m. All subjects will be fasting for at least 10 h overnight prior to dosing in both treatment periods. Subjects assigned to be fasting prior to dosing will remain fasting until lunch and subjects assigned to be fed prior to dosing will start their high-fat breakfast 30 minutes prior to the dose. Lunch will be provided 4 h after dosing for all subjects.

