12. DRUG CONCENTRATION MEASUREMENTS

12.1. Pharmacokinetic Blood Sampling

18 venous blood samples (volume of 2.7 mL each, total volume of approximately 48.6 mL) will be collected into pre-cooled lithium heparin tubes during each period, according to the following schedule:

Table 6: Blood Sampling for Pharmacokinetic Assessments During each Period

Blood Sample Number	Time from Dosing
1	Pre-dose (within 60 minutes prior to dosing)
2	00:15
3	00:20
4	00:30
5	00:45
6	01:00
7	01:30
8	02:00
9	02:30
10	03:00
11	04:00
12	06:00
13	08:00
14	12:00
15	14:00
16	16:00
17	24:00
18	48:00

The pre-dose blood samples will be collected within 60 minutes prior to dosing. The post-dose blood samples will be collected within +/-1 minute from the scheduled sampling time. The clock time will be recorded and reported for all blood draws and all subjects. A deviation greater than +/- 2 minutes will be reported as a protocol deviation and its cause will be recorded.

In case blood sampling for pharmacokinetics and other procedures coincide in time, blood draws will have priority unless other procedures are necessary for assuring subject's safety.

Immediately upon sampling, the blood sample for pharmacokinetic analysis will be identified with a bar-coded label bearing details of study number, subject number, study phase/period, sampling time point, sample type and a unique 9-digit identification number. The samples will be logged and then centrifuged at 1500 x g, 4°C for 10 minutes. Two equal aliquots of plasma will be transferred to polypropylene tubes labeled identically to the original blood sample (except sample type being plasma instead of whole blood) and logged when stored at approximately -20°C, pending analysis.

The blood samples will be placed on ice immediately and centrifuged within 60 minutes of being taken.

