15.7. Pharmacokinetic Analysis

Following logarithmic transformation, C_{max} , AUC_{0-t} , $AUC_{0-\infty}$ and Total A_e values will be subjected to an analysis of variance (ANOVA) including fixed effects for sequence, period, treatment and subject nested within sequence. Point estimates and 90% confidence intervals (CI) will be constructed for the contrasts between fed and fasted states using the residual mean square error obtained from the ANOVA. The point and interval estimates will be back-transformed to give estimates of the ratios of the geometric least squares means (LSmean) and corresponding 90% CI. In addition, estimated geometric means will be presented.

A comparison of T_{max} will be performed using the Wilcoxon Signed-Rank test. In addition, the Hodges-Lehmann estimate of the median difference in T_{max} and 95% CI will be presented.

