- All hypothesis testing will be carried out at the 5% (2-sided) significance level unless stated otherwise.
- P-values will be rounded to four decimal places. P-values less than 0.0001 will be reported as <0.0001 in tables.
- Generally, character values will be left aligned and numeric values will be decimally aligned.
- If any of the assumptions underlying the formal statistical methods proposed are violated during the analysis of the final data, alternative statistical methods will be used and any changes documented in the statistical methods section of the clinical study report (CSR), including the rationale for use.

- For numeric data which includes non-numeric values (e.g. PK data reported as BLQ or laboratory results reported as < 10 or >100) the following principles will be applied when summarising the data:
  - BLQ will be replaced with a zero.
  - Results reported as <x or >x will be treated as x.

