#### 11.4.4.1 Statistical Analysis of Urine PK Parameters

Following logarithmic transformation, Total  $Ae_{0-48h}$  values will be subjected to an analysis of variance (ANOVA) including fixed effects for sequence (treatment schedule), period, treatment and subject nested within sequence. Point estimates and 90% confidence intervals (CI) will be constructed for the contrasts between fed and fasted states using the residual mean square error obtained from the ANOVA. The point and interval estimates will be back-transformed to give estimates of the ratios of the geometric least squares means (LSmean) and corresponding 90% CI. In addition, estimated geometric means will be presented.

The statistical analysis of the urine PK parameter will be performed using the Urine Excretion Set and also the Safety Set should they differ. Geometric LSmeans will be presented to three significant figures and the ratios and 90% CIs will be presented to 2 decimal places.

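### Is it a flaw that Tmax is compared without the period adjustment used for Cmax, AUC and urinary excretion?

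*SAP*

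**What the plan says.** Protocol 15.7 states: "A comparison of T_{max} will be performed using the Wilcoxon Signed-Rank test". SAP 11.4.2.1 repeats it (the comparison "will be performed using the Wilcoxon Signed-Rank test"), and both add a Hodges-Lehmann estimate of the median difference with a 95% CI. Neither mentions period for this endpoint.

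The other fed-fasted comparisons use a crossover ANOVA on the log scale. For total urinary excretion, SAP 11.4.4.1 describes it as "including fixed effects for sequence (treatment schedule), period, treatment and subject nested within sequence"; SAP 11.4.2.1 gives Cmax and both AUCs the same terms.

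Tmax is a secondary variable (SAP 4.2), and no acceptance limit or decision rule is attached to it. Twelve subjects are randomised, six per schedule (SAP 3.5).

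**The concern.** Schedule A is fed then fasted, and Schedule B the reverse. If Tmax drifts between periods, the fed-minus-fasted difference moves one way in A and the other way in B. Pooling the two schedules puts the drift into the spread of the differences and can widen the interval. If the schedules end up unequal in size, the drift no longer cancels and the estimate shifts. Imbalance is possible: withdrawals for drug-related adverse events are not replaced (protocol 6.3), and the PK Set requires both doses and usable profiles (SAP 6.2).

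The plan removes period from every modelled comparison but not from this one, and gives no reason. At stake would be the precision, and to a lesser degree the accuracy, of a reported secondary estimate.

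**Working it through.** **Inputs from the documents.** Tmax was 0.75 h fasted and 2.75 h fed in the earlier food study "in the original marketed formulation during the fed and fasted states" (protocol 2.2, Table 3), a shift of 2.75 - 0.75 = 2.00 h. Sampling is every 30 minutes from 1 to 3 h ("Table 6: Blood Sampling for Pharmacokinetic Assessments During each Period"). The plan states no precision for Tmax, so there is no Tmax figure to reproduce. Its one sample-size figure, 4 subjects for AUC0-inf, does reproduce (power 0.888 at n = 4, 0.447 at n = 3), but does not bear on Tmax.

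**Assumptions.** The documents give neither the SD of the within-subject Tmax difference (s) nor a period effect (p, Period 2 minus Period 1). Ranges used: s = 0.6 to 0.9 h, and about 1.4 h in a run with Tmax placed on the sampling times; p = 0 to 1 h. The planned interval is taken as the one-sample Hodges-Lehmann interval that goes with the signed-rank test. The adjusted one is the halved two-sample version on period differences. Both use exact limits, with 20,000 simulated trials per case.

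**Bias.** With true shift d, the expected difference is d - p in Schedule A and d + p in Schedule B. The pooled mean is d - p(nA - nB)/n.
- 6:6: zero.
- 6:5: 0.25/11 = 0.023 h (1.4 min) at p = 0.25 h; 0.5/11 = 0.045 h (2.7 min) at p = 0.5 h.
- 6:4: 0.25 x 2/10 = 0.05 h (3 min); 0.5 x 2/10 = 0.10 h (6 min).

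The simulated biases agree (about 0.02 to 0.11 h). The largest is about 5% of the 2 h shift and well under one sampling interval.

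**Width.** At 6:6 the pooled variance is s^2 + p^2. With no period effect the planned interval is 0.97 times the adjusted one, so approximately ratio = 0.97 x sqrt(1 + (p/s)^2). It exceeds 1 when (p/s)^2 > (1/0.97)^2 - 1 = 0.063, that is, p > 0.25 s. At 6:5 the starting ratio is 0.89, and (1/0.89)^2 - 1 = 0.262 gives p > 0.51 s. In hours, break-even at 6:6 is 0.15 h (s = 0.6), 0.23 h (s = 0.9) and 0.35 h (s = 1.4).

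Simulated ratio of widths, planned / adjusted (below 1 means the planned interval is narrower):

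| p (h) | 6:6, s 0.6-0.9 | 6:5 and 6:4, s 0.6-0.9 | 6:6, grid, s about 1.4 | 6:5, grid, s about 1.4 |
|---|---|---|---|---|
| 0 | 0.97 | 0.88-0.89 | 0.93 | 0.89 |
| 0.1 | 0.975-0.985 | 0.89-0.90 | not run | not run |
| 0.25 | 1.01-1.06 | 0.92-0.97 | 0.95 | 0.90 |
| 0.5 | 1.13-1.31 | 1.02-1.20 | 1.00 | 0.94 |
| 1 | 1.55-2.17 | not tabulated | 1.20 | 1.12 |

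With normal errors and s = 1.4 h, the ratios at p = 0.5 h are 1.04 (6:6), 0.95 (6:5) and 0.94 (6:4).

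**Validity and precision of the estimate.** Planned coverage at 6:6 is 0.957-0.959, 0.965-0.972 and 0.977-0.990 at p = 0, 0.25 and 0.5 h. A period effect therefore makes the interval conservative, not too short. The SD of the point estimate at 6:6 is essentially the same for both methods (s = 0.6 h: 0.179 v 0.181 h at p = 0; 0.181 h for both at p = 0.5 h).

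**Detection of a 2 h shift.** The planned lower limit is above zero in at least 98.5% of trials in all 24 cases with s = 0.6 or 0.9 h. On the grid with s about 1.4 h, it is above zero in at least 99.9% up to p = 0.5 h and at least 96.5% at p = 1 h (6:6, 6:5 and 7:5). A 6:4 split with both s = 1.4 h and p = 1 h lies outside these runs and would do less well.

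**How large could p be?** The design gives no reason to expect much. Doses are 48 h apart against a half-life of 4.77 h at most in Table 3 (48/4.77 = 10.1 half-lives), and protocol 5.2 says this washout "is deemed sufficiently long to avoid any relevant carry-over effect". Dosing is at about 9:00 in both periods, and "All subjects will be fasting for at least 10 h overnight prior to dosing in both treatment periods" (protocol 8.8). A 0.5 h effect would be two thirds of the whole fasted Tmax (0.5/0.75 = 0.67).

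**The case for a change.** The best argument for adjustment is that it is cheap insurance. At the planned 6:6 it costs about 3% in width if there is no period effect, and saves 13-31% at 0.5 h when s is 0.6-0.9 h. At 6:4 with p = 0.5 h and s = 0.6 h, it also lowers the root mean squared error from 0.227 to 0.202 h. SAP 10.1 allows other methods if assumptions fail but names none for Tmax, so a period-adjusted analysis not planned now would be chosen after seeing the data. Comparing Tmax is a named secondary objective.

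The asymmetry with the ANOVA is real, and the adjusted method is better if the period effect is large relative to s. The insurance argument is weaker than it looks:

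- The 13-31% depends on a small s. At s = 1.4 h it falls to about 4% at 6:6 and reverses at 6:5 and 6:4.
- Bias arises only when the sequences are unequal, and there the adjusted interval is 12-13% wider with no period effect and still 3-9% wider at 0.25 h. Part of this is discreteness of the exact limits (attained level 96.97% v 95.80% at 6:5), but that is the interval that would be reported.
- Imbalance is held down because replacements take the schedule of the subject replaced (SAP 3.6). The Tmax analysis is also repeated on the Safety Set if that differs from the PK Set (SAP 11.4.2.1).
- The construction of the Hodges-Lehmann interval cannot be called unspecified. SAP 11 refers to the table shells for specifications, and these are blacked out in the public copy.

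**Conclusion.** The concern does not hold. The planned Tmax analysis is valid, prespecified and identical in protocol and SAP. The sequence term in the ANOVA has no counterpart to miss here, because within-subject differencing removes it. Omitting the period adjustment costs precision only if the period effect exceeds about 0.25 s at 6:6 or about 0.5 s at 6:5. With a smaller effect, which the design makes more likely, the planned interval is the narrower one. Bias is zero at 6:6 and about 1 to 6 minutes at 6:5 or 6:4 for effects of 0.25 to 0.5 h, on a 2 h shift.

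Making a period-adjusted method the main analysis would lose some precision where the trial is most likely to be, and gain it only under a large, undocumented period effect, on a secondary endpoint with no decision rule. That is a preference between two sound methods.

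This rests on assumed values of s (0.6 to 1.4 h) and p (0 to 1 h), and on the one-sample reading of the Hodges-Lehmann interval. It would need another look only if s were small and the period effect were 0.5 h or more.
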